1 PROTOCOL SUMMARY

1.1 Protocol Synopsis

Sponsor: Ampio Pharmaceuticals, Inc.	Investigational Product: Ampion™						
Title of Study: A Randomized, Double-Blinded, Placebo-Controlled Phase II Study to Evaluate the Safety and Efficacy of Intravenous Ampion in Adult COVID-19 Patients Requiring Oxygen Supplementation							
Rationale: The severe acute respiratory syndrome coronavirus 2 (SARS-CoV-2) has resulted in the pandemic spread of coronavirus disease 2019 (COVID-19), which has a high rate of infection, has a high rate of hospitalization, has overwhelmed healthcare systems, and can be fatal. Ampion is the low molecular weight filtrate of human serum albumin with the in vitro ability to modulate inflammatory cytokine levels. Ampion has the potential to improve clinical outcomes for COVID-19 patients by reducing inflammatory cytokines correlated with the disease. This study aims to evaluate Ampion and clinical outcomes in patients with COVID-19 who require supplemental oxygen. The data from this study will inform decisions for the Ampion clinical development.							
Lead Investigators: [name], PhD, USA							
Number of Sites: Approximately 10 sites							
Indication: Adult COVID-19 patients on supplemental oxygen							
Number of Participants: Sample size is approximately 200 patients, randomized 1:1 for Ampion or control. An interim analysis will be conducted at 30 participants, randomized 1:1 for Ampion or control to allow for sample size re-estimation as needed.							
Treatment Groups: There are two planned treatment arms:							

Treatment Arm	Investigational Treatment	

Active	IV Ampion for 5-days	

Control	IV Placebo for 5-days	

		Treatment Arm	Investigational Treatment	Active	IV Ampion for 5-days	Control	IV Placebo for 5-days
Treatment Arm	Investigational Treatment						
Active	IV Ampion for 5-days						
Control	IV Placebo for 5-days						

Sponsor: Ampio Pharmaceuticals, Inc.	Investigational Product: Ampion™
Objectives and Endpoints:	
Objective	Endpoint
Primary	
Assess the effect of Ampion compared to placebo on prevention of need for mechanical ventilation or death	
Occurrence of mechanical ventilation or death by Day 28.
Secondary	
Assess the effect of Ampion compared to placebo on safety	
Incidence of adverse events (AEs) and serious adverse events (SAEs) from baseline to Day 60.
Assess the effect of Ampion compared to placebo on hospital stay	
Hospital length of stay (LOS) from admission to discharge.
Assess the effect of Ampion compared to placebo on oxygen use	
Change from baseline in oxygen use, blood oxygen saturation, and oxygen flow rate from baseline through Day 5.
Assess the effect of Ampion compared to placebo on duration of respiratory failure to ventilator-free days	
Percentage of participants who progress to respiratory failure (i.e., need for mechanical ventilation, ECMO, non-invasive ventilation) by Day 28.
Assess the effect of Ampion compared to placebo on intensive care	
Percentage of participants who require Intensive Care Unit (ICU) admission by Day 28.ICU-free days through Day 28.ICU LOS from ICU admission to discharge.
Assess the effect of Ampion compared to placebo on clinical improvement	
Change in ordinal scale from baseline through Day 7.Change in ordinal scale from baseline to hospital discharge or Day 14 (whichever occurs first).Change in ordinal scale from baseline to hospital discharge or Day 28 (whichever occurs first).
Assess the effect of Ampion compared to placebo on clinical health	
Change in NEWS2 score from baseline through Day 5.Change in NEWS2 score from baseline to hospital discharge.
Assess the effect of Ampion compared to placebo on cytokine profile	
Modulation of cytokine levels from baseline to Day 5

Study Design:

Overall Design

This is a Phase II randomized, double-blinded, placebo-controlled study in adult participants with COVID-19 who require supplemental oxygen.

Screening

Interested participants will sign the appropriate informed consent document(s) prior to completion of any study procedures. The investigator will review symptoms, risk factors and other non-invasive inclusion, including COVID testing, and exclusion criteria prior to any study procedures. If the participant is eligible after this review, then the site will perform the necessary, if any, study procedures to confirm eligibility.

Treatment and Assessment

Participants will be randomized to active treatment or control, following an equal allocation to treatment arms. Given the changing nature of the pandemic, periodic adjustments to the allocation ratio may be made in an effort to achieve equal allocation across the treatment arms at the end of the enrollment. There are two planned treatment arms:

Treatment Arm	Investigational Treatment
Active	IV Ampion for 5-days
Control	IV Placebo for 5-days

The general sequence of events during the treatment and assessment period:

- Complete baseline procedures and sample collection
- Participants are randomized to receive either Ampion or a placebo.
- Participants receive study intervention (active or placebo) as an IV infusion for 5 days.
- Complete safety monitoring and post-infusion sample collection.

The Schedule of Assessments is shown in [Section 1.2](#). Visit types are described as follows:

Study Day	Visit Description	Visit Type
0-5	Treatment	Site
28, 60	Follow-up	Telephone
Early discontinuation	ED	May be conducted at site or via telephone

Post-Treatment Follow-up

Post-treatment follow-up will occur after Day 5 to assess clinical status and for adverse events.

Disclosure Statement

Assigned treatment, active or placebo, will be blinded to the patients, clinicians, and the investigators conducting the study.

Sponsor: Ampio Pharmaceuticals, Inc.	Investigational Product: Ampion™

Data Safety Monitoring Board
 
There will be a Data Safety Monitoring Board (DSMB). Safety, including incidence of AEs/SAEs will be evaluated by a DSMB throughout the study.
	

Diagnosis and Main Criteria for Inclusion:
 
1. Male or female, ≥ 18 years old2. Diagnosed with COVID-19, as evaluated by laboratory diagnostic test or diagnosis based on radiological clinical findings.3. Baseline severity categorization of severe or critical COVID-19 infection per FDA Guidance for developing drugs and biological products for COVID-19 (February 2021):
a) Severe COVID-19:
• Symptoms suggestive of severe systemic illness with COVID-19, which could include shortness of breath or respiratory distress• Clinical signs indicative of severe systemic illness with COVID-19, such as respiratory rate ≥ 30 per minute, heart rate ≥ 125 per minute, SpO₂ $\leq 93\%$ on room air at sea level (SpO₂ $\leq 90\%$ at altitude) or PaO₂/FiO₂ ≤ 300b) Critical COVID-19:
• Oxygen delivered by high-flow nasal cannula (heated, humidified, oxygen delivered via reinforced cannula at flow rates > 20 L/min with fraction of oxygen ≥ 0.5) or• Non-invasive mechanical or endotracheal mechanical ventilation4. Informed consent obtained from the patient or the patient's legal representative.	

Main Criteria for Exclusion:
 
1. As a result of the medical review and screening investigation, the Principal Investigator considers the patient unfit for the study and/or progression to death is imminent and inevitable irrespective of the provision of treatments.2. Clinical diagnosis of respiratory failure (therapy not able to be administered in setting of resource limitation)3. Shock defined by systolic blood pressure <90 mm Hg, or diastolic blood pressure <60 mm Hg or requiring vasopressors. Vasopressor therapy is exclusionary if used to treat shock. Subjects receiving low dose vasopressors to maintain renal perfusion are eligible.4. Multi-organ dysfunction/failure5. Patient has severe chronic obstructive or restrictive pulmonary disease (COPD) (as defined by prior pulmonary function tests), chronic renal failure (only exclusionary if subject is currently on renal replacement therapy, i.e., subjects receiving peritoneal dialysis, hemodialysis, ultrafiltration are ineligible), or significant liver abnormality (e.g., cirrhosis, transplant, etc.).	

Sponsor: Ampio Pharmaceuticals, Inc.	Investigational Product: Ampion™

6. Patient has chronic conditions requiring chemotherapy or immunosuppressive medication (only exclusionary if subject is currently receiving a high dose or therapy for transplantation, e.g., subjects receiving low dose inhaled or oral steroids for asthma are eligible).
 
7. A history of allergic reactions to human albumin (reaction to non-human albumin such as egg albumin is not an exclusion criterion) or ingredients in 5% human albumin (N-acetyltryptophan, sodium caprylate).
 
8. Prolonged QT interval.
 
9. Patient has known pregnancy or is currently breastfeeding.
 
10. Patient planning to become pregnant, or father a child, during the treatment and follow-up period and/or is not willing to remain abstinent or use contraception.
 
11. Participation in another clinical trial (not including treatments for COVID-19 as approved by the FDA through expanded access, emergency, or compassionate use), or participation in a trial such that enrollment in this study would fall within the time frame of the half-life of the other investigational product(s).
	
Test Product, Dose, and Mode of Administration:	

Participants in the active arm will receive a 250cc daily dose of Ampion as an IV infusion for 5 days. The daily dose of Ampion will be delivered by IV twice daily (125cc/dose), every 12 hours, for 5 days.
 
All subjects receiving test product will also receive the standard of care (SOC) for COVID-19, which includes:
 
• Oxygen administration to maintain oxygen saturation of 90% or greater.• Nursing physical that may include review of neurological, pulmonary, cardiac gastrointestinal, and urinary assessment at least daily.• Vital monitoring (heart rate, blood pressure, temperature, respiratory rate, SpO2) daily• Telemetry monitoring to evaluate heart rhythm and rate.• Diet as tolerated to satisfy nutritional needs.• Treatments for COVID-19 symptoms including antibiotics, cough suppressants/expectorants, anti-coagulants, fever reducers/pain killers, anti-nausea drugs, and/or bronchodilators.• Treatments for COVID-19 as approved by the FDA including expanded access, emergency, or compassionate use (i.e., remdesivir, dexamethasone, convalescent plasma). 
Medications will be recorded as concomitant medication, tabulated, and compared among groups.
	
Reference Therapy, Dose and Mode of Administration:	

Sponsor: Ampio Pharmaceuticals, Inc.	Investigational Product: Ampion™

Participants in the control arm will receive a 250cc daily dose of Placebo as an IV infusion for 5 days. The daily dose of Placebo will be delivered by IV twice daily (125cc/dose), every 12 hours, for 5 days.
 
All subjects receiving placebo will also receive the SOC for COVID-19 as described previously.
	
Study Duration: Treatment: 5 days Follow-up: 60 days	

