3 STUDY DESIGN

3.1 Study Design Overview

This is a Phase II randomized, double-blinded, placebo-controlled study to evaluate the safety and efficacy of IV Ampion in participants with COVID-19 who require supplemental oxygen.

Interested COVID-19 patients will sign the appropriate informed consent document(s) prior to completion of any procedures. The investigator will review inclusion and exclusion criteria prior to any invasive procedures. If the patient is eligible after this review, the site will perform the necessary, if any, study procedures to confirm eligibility.

Participants will be randomized 1:1 to active or placebo using a random allocation sequence stratified by disease severity. The general sequence of events during the treatment and assessment period:

- Complete baseline procedures and sample collection.
- Participants are randomized to Ampion or placebo.
- Participants receive study intervention (active or placebo) through IV infusion for 5 days.
- Complete safety monitoring, study procedures, and sample collection through Day 60.

All subjects receiving test product will also receive the standard of care (SOC) for COVID-19, which includes:

- Oxygen administration to maintain oxygen saturation of 90% or greater.
- Nursing physical that may include review of neurological; pulmonary; cardiac; gastrointestinal; and urinary assessment at least daily during treatment.
- Vital monitoring (heart rate, blood pressure, temperature, respiratory rate, SpO₂) at least daily during treatment.
- Telemetry monitoring to evaluate heart rhythm and rate.
- Diet as tolerated to satisfy nutritional needs.
- Treatments for COVID-19 symptoms including antibiotics, cough suppressants/expectorants, anti-coagulants, fever reducers/pain killers, anti-nausea drugs, and/or bronchodilators.
- Treatments for COVID-19 as approved by the FDA including expanded access, emergency, or compassionate use (i.e., remdesivir, dexamethasone, convalescent plasma).
- Medications will be recorded as concomitant medication, tabulated, and compared among groups.

The clinical effects, safety, and tolerability of treatment will be evaluated from baseline through Day 60. Evaluations at screening and during the 5-day treatment occur in person. Evaluations after the 5-day treatment to the end of the study (days 7 to 60) will typically occur via telephone contact unless the patient is in an inpatient setting.

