3.4 Blinding and Randomization

The treatment in this study will be blinded to the subjects, investigators, any individual conducting the study (e.g., nursing and pharmacy staff) and clinical study personnel. Participants will be assigned to treatment by a randomization schedule developed and maintained by an independent statistician.

Participants are randomized to active or control, following an equal allocation to treatment arms, stratified by COVID-19 disease severity (severe or critical as defined in [Section 4.4](#)).

Study drug and placebo will be provided as blinded investigational product (IP) with appropriate labeling to link to the randomization code. Where required, safety personnel and/or investigator may be unblinded to a particular subject's treatment assignment to meet reporting requirements to Regulators.

A data management plan and statistical analysis plan will be approved by the sponsor prior to unblinding study data.

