9.4 Study Endpoints

9.4.1 Primary Endpoint

The primary endpoint assesses the effect of Ampion compared to placebo on the prevention of need for mechanical ventilation or death. This is measured as the occurrence of mechanical ventilation or death by Day 28.

Let π_A and π_S represent the rate of this outcome for Ampion and control during the first 28 days after randomization. Then it is desired to demonstrate that the mechanical ventilation and death rate for Ampion is different than the corresponding rate for the control. Formally, this is presented as:

$$H_0: \pi_A = \pi_S \text{ versus } H_A: \pi_A \neq \pi_S$$

This will be tested utilizing the appropriate chi-square test or Fisher's exact test utilizing PROC FREQ with the EXACT option, if necessary.

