2.4 Sample Size

The trial is designed to enroll up to approximately 200 patients across two treatment arms (active or control), with 100 subjects per arm, randomized 1:1 using a random allocation sequence stratified by COVID-19 disease severity (severe or critical). An interim analysis of the data is planned after 30 subjects (approximately n=15 subjects per arm) to evaluate the relative effect. At the interim analysis, the sample size may be re-estimated to determine the additional number of patients required for adequate power to meet the chosen effect size for the primary endpoint.

The number of participants is selected based on the effects observed for the primary endpoint, prevention of need for mechanical ventilation or death prior to day 28. A study recently reported in Lancet Respiratory Medicine with 243 hospitalized patients receiving the placebo for COVID-19 found 22% did not achieve day 28 ventilation-free survival (Lancet Respir Med 2021; [https://doi.org/10.1016/S2213-2600\(21\)00494-X](https://doi.org/10.1016/S2213-2600(21)00494-X)). In the AP-014 study, a lower rate (8%) was observed for subjects receiving inhaled Ampion. Assuming the same proportions (8% for Ampion and 22% for control) by Day 28, with 100 subjects per group, a two-sided 5% significance level, and using a z-test with unpooled variances, then under binomial enumeration the power to detect this difference is about 81.3%.

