3. STUDY ENDPOINTS AND ANALYSES

Statistical Analysis Plan (SAP) for Clinical Study AP-017

3.1 Primary Endpoint:

The primary endpoint assesses the effect of Ampion compared to placebo on prevention of need for mechanical ventilation or death prior to day 28. This is measured as the occurrence of mechanical ventilation or death by Day 28.

Let π_A and π_S represent the rate of this outcome for Ampion and control during the first 28 days after randomization. Then it is desired to demonstrate that the mechanical ventilation and death rate for Ampion is different than the corresponding rate for the control. Formally, this is presented as:

$$H_0: \pi_A = \pi_S \text{ versus } H_A: \pi_A \neq \pi_S$$

This will be tested utilizing the appropriate chi-square test or Fisher's exact test utilizing PROC FREQ with the EXACT option, if necessary.

Also, the median time to mechanical ventilation or death will be tested for difference between the two groups via the log-rank test. The test will be performed using PROC LIFETEST. The time to event distributions in each group will be estimated using the method of Kaplan and Meier.

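### The synopsis permits open-ended changes to the allocation ratio that the rest of the plan does not describe; if used while event rates drift, they can bias the unstratified primary test in either direction

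*Protocol*

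**What the plan says.** The Treatment and Assessment part of the synopsis (Protocol 1.1) starts from equal allocation. It then adds, with the reason "Given the changing nature of the pandemic", that "periodic adjustments to the allocation ratio may be made in an effort to achieve equal allocation across the treatment arms" by the time enrolment ends. It does not say what would prompt an adjustment, how large it could be, how often it could happen, who would decide, or what information that person could see.

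Nothing else in the plan mentions a ratio change:

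- The participant-number entry of the same synopsis gives 1:1.
- Protocol 3.1: "Participants will be randomized 1:1 to active or placebo using a random allocation sequence stratified by disease severity".
- Protocol 3.4 gives equal allocation stratified by severity, and says: "Participants will be assigned to treatment by a randomization schedule developed and maintained by an independent statistician".
- Protocol 4.1 and 9.1 repeat 1:1 with 100 per arm.
- SAP 2.3, 2.4 and 6.1 also give only 1:1 or equal allocation. SAP 9, which lists changes from the protocol, does not mention the ratio.

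The primary analysis is the same in Protocol 9.4.1 and SAP 3.1: "This will be tested utilizing the appropriate chi-square test or" Fisher's exact test, with no stratum, period or covariate. SAP 3.1 adds that "the median time to mechanical ventilation or death will be tested for difference between the two groups via the log-rank test", again with no strata named. The time trends examined in SAP 3.2 are trends over visits within a patient, not over calendar time.

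**The concern.** Equal arm totals at the end of enrolment do not make the arms comparable if they were filled at different times. If early patients go mainly to one arm and later patients mainly to the other, the arms sample different phases of the pandemic. A crude comparison then attributes part of any change in background risk to the drug.

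The reason given for the clause makes this relevant, because a changing pandemic is the setting in which event rates may move. Background care may move too: the plan's standard of care follows FDA approvals and authorisations (Protocol 3.1).

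At stake are the type I error of the primary test and, in the opposite direction, its power. There is also a plain inconsistency: the synopsis permits a procedure that the protocol body and SAP neither describe nor analyse.

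**Working it through.** **The plan's own figure.** Inputs from Protocol 4.1 and 9.1 and SAP 2.4: 8% versus 22%, 100 per arm, two-sided 5%, unpooled z-test by binomial enumeration. Exact enumeration gives 81.28%, which agrees with the stated 81.3%. That calculation assumes one event rate per arm for the whole trial.

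**Bias formula.** Take two enrolment periods of 100 patients with final totals 100 and 100. Let a1 and c1 be the shares of the Ampion and control arms enrolled in period 1, and p1 and p2 the event rates in the two periods for a drug with no effect. Then

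bias (Ampion minus control) = (a1 − c1) × (p1 − p2).

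It is zero if the ratio never changes (a1 = c1) or if there is no drift (p1 = p2). The period split, ratios and drift below are all assumptions, because the documents give none.

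By hand, for 40:60 then 60:40 with 30% then 14%:

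- Ampion: (40 × 0.30 + 60 × 0.14)/100 = 20.4%
- Control: (60 × 0.30 + 40 × 0.14)/100 = 23.6%
- Difference: −3.2 points, which equals (0.40 − 0.60) × 0.16.

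**Type I error.** Simulated null trials, two-sided level 0.049 (the final level in SAP 6.1), pooled z-test (the chi-square test) against a Cochran-Mantel-Haenszel (CMH) test stratified by period:

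| Event rate, period 1 then 2 | Ampion:control, period 1 then 2 | Bias (points) | Crude test | CMH by period |
|---|---|---|---|---|
| 22% then 15% | 40:60 then 60:40 | −0.20 × 7 = −1.4 | 5.4–5.5% | 4.8–5.0% |
| 22% then 15% | 33:67 then 67:33 | −0.34 × 7 = −2.4 | 6.8–6.9% | 4.8–5.0% |
| 30% then 14% | 40:60 then 60:40 | −0.20 × 16 = −3.2 | 7.8–7.9% | 4.8–5.0% |
| 30% then 14% | 33:67 then 67:33 | −0.34 × 16 = −5.4 | 14.4–14.6% | 4.8–5.0% |

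The excess is almost all on one side. In the third row, false positives favouring Ampion are 7.4%, against a nominal 2.45% (half of 4.9%).

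**Opposite direction.** With 60:40 then 40:60 and the same fall from 30% to 14%, the bias is +3.2 points, against Ampion. At the planned relative risk of 8/22, the Ampion rates are 30% × 8/22 = 10.9% and 14% × 8/22 = 5.1%. The expected crude rates are:

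- Ampion: 0.60 × 10.9% + 0.40 × 5.1% = 8.6%
- Control: 0.40 × 30% + 0.60 × 14% = 20.4%

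The expected difference shrinks from 14.0 points (22% − 8%) to 11.8. Simulated power at the 5% level falls from about 81–82% with fixed 1:1 to about 68%. CMH by period recovers about 80–81%.

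**Smaller uses of the clause** (5% level):

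- Ratio changed after the first 30 patients (20:10, then 80:90), rates 27% then 17% or 30% then 14%: bias 0.10 × 10 = 1.0 to 0.10 × 16 = 1.6 points. Type I error is 5.5–5.9%.
- Simple 1:1 randomisation of the first 100 patients, then correction to 100 and 100: mean bias zero. Type I error is 5.3–5.5% under the same drifts, and 4.9–5.3% across the runs at level 0.049.

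**The case against.** The strongest reply is that the clause is permissive and its stated purpose is benign. It says adjustments may be made, starts from equal allocation, and aims only at equal totals. Repairing a chance imbalance gives no average bias and close to nominal error, as shown above. Large swings would be unusual in that use: with simple 1:1 randomisation of 100 patients, a split of 40:60 or worse has probability 5.7%, and 33:67 or worse 0.09%. All of this stands.

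A reader might therefore go too far in three ways:

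- **That the clause does bias this trial, or that its type I error is about 14.5%.** The documents report no ratio change and give no drift. Bias needs both, and its sign depends on which arm is favoured early and whether rates rise or fall. The larger figures rest on assumed ratios as well as assumed drift.
- **That the clause is redundant because permuted blocks already keep the arms equal.** The documents never mention blocks; they say only that the sequence is stratified by severity.
- **That adjusting the ratio would expose assignments.** Someone must track arm totals, and nobody is named to do so. But the schedule sits with an independent statistician, the product is blinded, and tracking totals needs no outcome data. This is a minor point.

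The reply does not remove the rest. The stated reason is the pandemic, not chance imbalance. Nothing limits the size or use of an adjustment, and no analysis would correct for one.

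**Conclusion.** The concern holds in conditional form. The synopsis grants an unbounded permission that conflicts with the 1:1 or equal allocation stated elsewhere, and the planned tests have no safeguard if it is used. A ratio change combined with event-rate drift can bias the crude primary comparison either way, and equal final totals do not prevent this.

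In the scenarios tried, the effect runs from negligible (repair of chance imbalance, or mild drift at 40:60) to a few percentage points of extra type I error, or about 13 points of lost power (81% to 68%) with a 60:40 swing and a halving of the event rate. The 33:67 case is an extreme illustration. No single figure can be given for this trial. The stated power of 81.3% is not in dispute.

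**What to change.** Delete the sentence from the synopsis so that it agrees with the 1:1, severity-stratified allocation in Protocol 3.1, 3.4, 4.1 and 9.1 and in the SAP. If close balance is wanted, permuted blocks within severity stratum could be added. That would be a new specification, since the documents state none.

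If the ratio has been changed, or the sponsor wishes to keep the option:

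- State who may change the ratio, on what trigger and within what limit, blind to outcome data.
- Record the date of each change.
- Stratify the primary test (CMH) and the log-rank test by allocation period as well as severity.

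Stratifying the primary test by period restores about 4.9% type I error in the simulations; adding severity and stratifying the log-rank test were not simulated.

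Deleting the sentence costs one line and a possible final imbalance of a few patients, with no material loss of power. Stratifying after a real ratio change costs some power: about 79–81% at 60:40 then 40:60, and 76–78% at 67:33 then 33:67, against 81–82% with fixed 1:1.
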